5.2.3 Temozolomide

Arm 1: patients will be treated with ABT-414 1.0 mg/kg IV infusion over 30 to 40 minutes once every 2 weeks in combination with TMZ 150 mg/m² day 1 to 5, for the first 28-day cycle, with dose escalation to 200 mg/m² in subsequent cycles in case of adequate tolerance (CTCAE v.4 toxicity grade less than 2) and until one of the treatment withdrawal criteria has been met.

Arm 3B: Patients relapsing 16 weeks or more after the first day of the last TMZ cycle will be treated with TMZ 150 mg/m² on day 1 to 5 for the first 28-day cycle, with dose escalation to 200 mg/m² in subsequent cycles in case of adequate tolerance (CTCAE v.4 toxicity grade less than 2). Treatment will continue until one of the treatment withdrawal criteria has been met.

The dose of TMZ does not have to be adjusted unless there has been at least a 10% change in body weight; recalculation of TMZ dose for < 10% weight changes is allowed at the discretion of the Investigator.

5.3 Treatment duration

Treatment will be administered until one of the withdrawal criteria (section 5.4) has been met. Lomustine will be given for a maximum of one year. Administration of TMZ with ABT-414 will continue if tolerated, and patients receiving treatment for more than 12 months will be evaluated and assess the risk of prolonged treatment.

5.4 Withdrawal criteria

Whatever the disease status, study treatment will be discontinued in case of:

- ◆ disease progression
- ◆ patient refusal
- ◆ intolerable toxicity precluding further protocol therapy
- ◆ patient's best interest
- ◆ start of any other anti-cancer agent/modality (surgery at recurrence is allowed)
- ◆ pregnancy

Patients discontinuing therapy in the absence of progression should not receive other cancer treatment before their disease progresses, unless this is clearly not in the interest of the patient. If, after treatment discontinuation, there is additional clinical information leading the investigator to conclude that the reason for discontinuation is no longer valid (except for toxicity), the subject may resume study treatment as long as no other chemotherapy, radiotherapy, immunotherapy, NovoTTF, or other treatment with antineoplastic intent has been received, with the exception of surgical intervention that yields histology not demonstrative of tumor progression. In case of toxicity in the combination arm that is

clearly attributable to either TMZ or ABT-414, that drug can be discontinued and the other can be continued. Patients that discontinue study treatment for toxicity, patient refusal and other reasons remain 'on study' and must be followed according to the follow-up schedule for progression, survival etc unless patient specifically withdraws consent from all further data collection for the study (this decision should be clearly documented e.g in the medical notes).

5.5 Dose and schedule modifications

In the combination arm, dose reductions or delays should be made for the likely causative agent. If in the combination arm one of the agents should be stopped for any reason other than PD, the patient can continue on the other single agent alone.

5.5.1 ABT-414

ABT-414 will be given by IV infusion over 30 to 40 minutes, on Days 1 (± 2 days) and 15 (± 2 days) of every 28-day cycle. Information about the ABT-414 formulation to be used in this study are presented below:

ABT-414 ^a	
Dosage Form	Lyophilized powder for reconstitution and intravenous admixture
Formulation	Vial
Strength (mg)	20 or 100

a. Information applicable to both ABT-414 and ABT-414 manufactured under two separate manufacturing processes (A and L).

Based upon results from the first clinical and preclinical safety pharmacology evaluation of ABT-414, experience with other inhibitors of EGFR, and experience with MMAF ADCs, potential toxicities may include fatigue, vomiting, thrombocytopenia, allergic reactions, rash, eye complaints, and liver function test abnormalities.

For all observed toxicities, except those listed below, subjects should be assessed for inter-current illness or other causes and treated as appropriate. For severe toxicities (Grade 3 or higher), dosing should be withheld until toxicity resolves to Grade 1 or less (unless otherwise indicated). Dose reduction of ABT-414 for Grade 3 toxicity will be at the discretion of the investigator and the study team. Re-initiation of ABT-414 may be considered at a reduced dose (to 1.0 mg/kg, 0.75 mg/kg, or 0.5 mg/kg) for grade 4 toxicities provided full recovery to grade 1 or less has occurred (unless otherwise indicated).

All dose reductions are permanent, except as listed below (hepatic laboratory abnormalities, section 5.5.1.4).

ABT-414 Dose Modification Table

Toxicity	Starting Dose	First Occurrence	Second Occurrence	Third Occurrence
Grade 1 or 2	1.0 mg/kg	No requirement for dose reduction	No requirement for dose reduction	No requirement for ABT-414 discontinuation
Grade 3	1.0 mg/kg	Can continue at 1.0 mg/kg or reduce to 0.75 mg/kg once the toxicity has resolved to grade 1 or baseline	Can continue at 0.75 mg/kg or reduce to 0.5 mg/kg once the toxicity has resolved to grade 1 or baseline	Can continue at 0.5 mg/kg once the toxicity has resolved to grade 1 or baseline or permanently stop ABT-414
Grade 4	1.0 mg/kg	Reinitiate treatment at 0.75 mg/kg once the toxicity has resolved to grade 1 or baseline	Reinitiate treatment at 0.5 mg/kg, once the toxicity has resolved to grade 1 or baseline	Permanently stop ABT-414

More aggressive dose reductions are always allowed if the investigator believes that it is in the best interests of the subject. While investigator discretion should be used for subject management with regards to toxicities, some suggested guidelines are included in the following sections.

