In the ongoing phase I study, as of April 29 2015, 40 subjects have been treated in Arm B and 42 in Arm C. Common treatment emergent AEs in at least 30% of subjects in Arm B included photophobia (15/37.5%), blurred vision (23/57.5%), nausea (19/47.5%), fatigue (17/42.5%) and headache (12/30%); in Arm C, they were blurred vision (25/59.5%) and fatigue (24/57.1%). Grade 3/4 AEs found in > 10% of subjects in Arm B included keratitis (5/12.5%), gamma GT elevation (4/10%) and decreased platelet (4/10%); in Arm C, the only grade 3/4 AEs of > 10% was keratitis (6/14.3%). Overall, in the 1.25 mg/kg dose cohort the grade 3/4 ocular toxicity rate was 27%. ABT-414 administration was suspended in those who developed grade 3/4 eye toxicity until symptoms recovered to grade 1, which took a median of 40 days.

Because of the high rate of significant eye toxicity and the need for drug interruption, the starting dose of ABT-414 for the present study for both Arm 1 and 2 will be 1.00 mg/kg.

Additional Safety Information:

Preliminary safety data were available for 488 subjects who received at least 1 dose of ABT-414 in 4 open-label studies at the most recent IB update (version 7.0). This Phase 2 Study M14-483 (INTELLANCE-2) in recurrent GBM is the only trial for which safety data from a control arm (TMZ or lomustine monotherapy) is available. Adverse events reported for more than 20% of subjects receiving ABT-414

were fatigue (34.9%), vision blurred (27.3%), headache and keratitis (25.0% for each), dry eye (24.4%) and corneal epithelial microcysts (22.1%). The majority of subjects who received ABT-414 (77.3%) experienced at least 1 Treatment Emergent Adverse Event coded to the Standard Organ Class of Eye Disorders. In addition to ocular side effects related to corneal epitheliopathy, treatment-emergent adverse events reported by $\geq 10\%$ of subjects in the ABT-414 treatment groups and $\geq 5\%$ more frequently than the lomustine/TMZ control group included headache, fatigue, constipation, and liver transaminase elevations (alanine aminotransferase and aspartate aminotransferase). The rate of constipation was mainly accounted for by the ABT-414/TMZ combination arm, for which the rate was similar to that of subjects receiving TMZ monotherapy.

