5.2 Initial dose and administration

5.2.1 ABT-414

ABT-414 will be given at dose level of 1.0 mg/kg by IV infusion over 30 to 40 minutes once every 2 weeks. The dose of ABT-414 does not have to be adjusted unless there has been at least a 10% change in body weight; recalculation of ABT-414 dose for < 10% weight changes is allowed at the discretion of the Investigator. Each configuration of ABT-414 drug product (Type A and/or Type L) that a subject receives during the study will be recorded.

Subjects will be closely monitored for treatment-related adverse events, especially allergic reactions, during the infusion. For the initial ABT-414 infusion, pre-infusion vital signs should be taken, direct observation is required for the first 15 minutes of the infusion, and subjects should be monitored for 1 hour post-infusion. For subsequent infusions, direct observation and monitoring post-infusion are not required; however, pre-infusion vital signs should still be taken.

Due to the risk of eye toxicity, each administration of ABT-414 should be given with steroid ophthalmic solution. The recommended type, dose, and schedule of eye drops is as follows: dexamethasone 0.1% solution (or equivalent corticosteroid solution), 2 drops (GTTS) in each eye (OU) every 8 hours to start 48 hours prior to ABT-414 dosing and continue for a total of 7 days (or 21 doses total). The type of ophthalmic solution used may vary depending on the availability of the solution at each location. A modification to the eye drop dosing or schedule based on ongoing clinical experience may be suggested.

Allergic reactions of any grade require interruption of ABT-414 treatment and management as described in section [5.5.1.1](#).

Subjects will not be treated at doses less than 0.5 mg/kg. If a subject requires a dose modification below 0.5 mg/kg, the subject will be discontinued from the study treatment.

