5.2.2 Lomustine

Arm 3A: Patients relapsing during TMZ treatment or within the first 16 weeks after the first day of the last TMZ cycle will be treated with lomustine 110 mg/m² on day 1 of every 42-day treatment period. However, similar to subjects who are randomized to ABT-414 plus TMZ (Arm 1), ABT-414 (Arm 2) or TMZ control (Arm 3B), scans (MRI) should be performed as per the schedule outlined for all other arms (see section 6.3.5). Treatment will continue until one of the treatment withdrawal criteria has been met. Lomustine will be given for a maximum of one year.

The doses may be rounded to the nearest 40 mg to accommodate tablet strengths. The dose of lomustine does not have to be adjusted unless there has been at least a 10% change in body weight; recalculation of lomustine dose for < 10% weight changes is allowed at the discretion of the Investigator.

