5.5.2 Lomustine

Patients requiring more than two consecutive lomustine dose reduction (i.e. only two dose reductions are allowed based on product labeling) will discontinue lomustine treatment. Study efficacy evaluations will not be modified because of dose delays. Dose modifications are based on toxicity during the prior treatment cycle. If multiple toxicities are seen, the dose administered should be based on the dose reduction required for the most severe grade of any single toxicity.

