5.5.2.1 Dose levels of lomustine

The lomustine dose will be rounded to the closest multiple available; the dosage is calculated based on BSA but a maximum dose (cap) is used. Two dose levels of lomustine will be used.

Dose	Dose mg/m ² q6 weeks
0	110 mg/m ² (cap 200 mg)
-1	90 mg/m ² (cap 160 mg)
-2	70 mg/m ² (cap 120 mg)

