5.5.2.1.1 Hematological toxicity

In general, the nadirs for hematological toxicity with lomustine are expected between days 28 and 35. In case of hematological toxicity grade 3 or 4 (according to CTCAE v. 4.0), the dosage of the next cycle will be reduced with one level. If the hematological toxicity does not recover within 4 weeks or if after recovery the hematological toxicity recurs at a subsequent cycle to grade ≥ 2 , lomustine treatment should be discontinued. No more than two dose reductions are allowed.

Administration of next cycle: If blood examination on day 42 or 43 (which may have been obtained in the prior 48 hours) show recovery of platelets above 100×10^9 and granulocytes counts above 1.5×10^9 , the next dose may be administered on day 43. If this is not possible, hematologic parameters will be repeated weekly and the next cycle will be given upon recovery of granulocytes and platelets. If after 4 weeks the patient has still not recovered, they should discontinue study treatment and stay on study until progression.

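### Protocol 5.5.1 gives two instructions for restarting ABT-414 after grade 4 toxicity: the text lists the adult starting dose as a reduced dose, and the table's grade 4 row does not contain it

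*Protocol*

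**What the plan says.** **ABT-414.** Protocol section 1.7 fixes the adult dose: "the starting dose of ABT-414 for the present study for both Arm 1 and 2 will be 1.00 mg/kg". Section 5.2.1 repeats it ("ABT-414 will be given at dose level of 1.0 mg/kg by IV infusion over 30 to 40 minutes once every 2 weeks"), as do the protocol summary, chapter 4, SAP section 4.2 and the starting-dose column of the Dose Modification Table.

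Section 5.5.1 then states the grade 4 rule twice. The paragraph before the table says that re-initiation "may be considered at a reduced dose (to 1.0 mg/kg, 0.75 mg/kg, or 0.5 mg/kg) for grade 4 toxicities", provided the toxicity has recovered to grade 1 or less. The grade 4 row of the table says, for a first occurrence, "Reinitiate treatment at 0.75 mg/kg once the toxicity has resolved to grade 1 or baseline". It gives 0.5 mg/kg for a second occurrence and permanent discontinuation for a third.

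**Lomustine.** Section 5.5.2 says that "only two dose reductions are allowed based on product labeling". Section 5.5.2.1 announces two dose levels, but its table has three rows: level 0 at 110 mg/m², level -1 at 90 mg/m² and level -2 at 70 mg/m². Section 5.5.2.1.1 lowers the next cycle by one level after grade 3 or 4 haematological toxicity. It also says that "if after recovery the hematological toxicity recurs at a subsequent cycle to grade" 2 or higher, lomustine is to be stopped, and it closes with the same ceiling of two reductions.

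**The concern.** For ABT-414, text and table in one section should give one answer to one question: at what dose may an adult restart after a grade 4 event? They do not. A site that restarts at 1.0 mg/kg can point to the list in the text, yet it departs from the table. Grade 4 is the most severe non-fatal grade, and section 1.7 explains that 1.00 mg/kg was chosen because of eye toxicity and the interruptions it caused. Two centres could therefore handle the same event differently, and a monitor could not say from the protocol which of them had deviated.

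For lomustine the problem is smaller. Two adjacent sentences both apply to a second grade 3 or 4 haematological event, and the section does not say how they interact.

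**Working it through.** No sample size, event count, power or alpha enters this point. The check sets the passages side by side.

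**1. Size of the listed reductions.** Inputs: adult starting dose 1.0 mg/kg (sections 1.7 and 5.2.1); listed restart doses 1.0, 0.75 and 0.5 mg/kg (text of 5.5.1). Reduction = 100 × (1 − listed dose / starting dose):

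- 1.0 mg/kg: 100 × (1 − 1.0/1.0) = 0%
- 0.75 mg/kg: 100 × (1 − 0.75/1.0) = 25%
- 0.5 mg/kg: 100 × (1 − 0.5/1.0) = 50%

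**2. Is 1.0 mg/kg a reduction for any adult?** The adult levels are 1.0, 0.75 and 0.5 mg/kg. Relative to a current dose of 1.0 it is no change. Relative to 0.75 it is an increase of 33% (1.0/0.75 = 1.33), and relative to 0.5 an increase of 100% (1.0/0.5 = 2). It is a reduction for no adult in Arms 1 or 2.

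**3. Text against table, grade 4.**

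| Occurrence | Text of 5.5.1 | Table in 5.5.1 |
|---|---|---|
| First | 1.0, 0.75 or 0.5 mg/kg | 0.75 mg/kg |
| Second | same list, not split by occurrence | 0.5 mg/kg |
| Third | same list, not split by occurrence | permanent discontinuation |

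**4. Can another passage reconcile them?**

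- The paragraph after the table lets the investigator reduce further than the table. It does not allow a smaller reduction, so it does not cover a restart at 1.0 mg/kg.
- The paediatric steps in Appendix I do not explain the list. Ages 0 to 5 step through 1.3, 1.0 and 0.67 mg/kg, which is a different set. For ages 6 to 17 the steps are 1.0, 0.75 and 0.5 mg/kg, so 1.0 is again the starting dose.
- Section 1.7 mentions 1.25 mg/kg as the dose recommended from the phase I study. Against that start, 1.0 mg/kg would be a 20% reduction (1 − 1.0/1.25). A carry-over is plausible, but no passage has adults in this trial starting at 1.25 mg/kg.

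**5. Which toxicities are affected.** The general paragraph excludes toxicities treated in later subsections. Severe allergic reactions (5.5.1.1.1) and grade 3 or 4 ocular toxicity (5.5.1.3) have their own rules, and hepatic laboratory abnormalities are handled in 5.5.1.4. Section 5.5.1.2, however, sends grade 3 or higher skin toxicity back to the guidance above it, so the conflict carries over there.

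**6. Lomustine: which levels can be reached?** The rules of 5.5.2 to 5.5.2.1.2 were applied to toxicity sequences over four cycles. Haematological grade 3 or 4 lowers one level, and recurrence at grade 2 or more stops the drug. Liver toxicity above grade 2 lowers one level. Any grade 4 non-haematological event, or non-haematological recurrence at grade 2 or more in the next cycle, stops the drug. At most two reductions are allowed.

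- Haematological toxicity alone: the lowest level reached is -1, because a repeat grade 3 or 4 event meets the stopping sentence.
- Liver toxicity alone: level -2 is reached, for example with grade 3 in cycles 2 and 4.
- One liver and one haematological event, both grade 3: level -2 is reached.

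The run takes recurrence to mean any haematological toxicity. If it means the same cell line only, a different cytopenia could also lead to a second reduction.

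**The case against.** **On ABT-414.** The sentence itself requires a reduced dose, so an adult restarted at 1.0 mg/kg would break that word as well as the table. It is therefore too strong to say that a site may freely follow either. The most frequent severe toxicity also lies elsewhere: keratitis was the only grade 3/4 event above 10% in Arm C of the phase I study (section 1.7), and ocular toxicity has its own rule. Both points stand and narrow the scope. They do not remove the mismatch, because 1.0 mg/kg is still printed as an allowed restart dose.

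**On lomustine recurrence.** A reader might infer that the recurrence rule contradicts the two reductions allowed. The documents do not support that. Two is a ceiling, not an entitlement; stopping earlier does not breach it, and level -2 can be reached through liver toxicity. The two sentences can also be read in sequence, the second qualifying the first. What stands is that the protocol does not say so.

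**On the lomustine cap.** A reader might also see a contradiction between section 5.2.2 and chapter 4, which give 110 mg/m² without a cap, and section 5.5.2.1, where "the dosage is calculated based on BSA but a maximum dose (cap) is used" (200 mg at level 0). Silence is not contradiction, and all of these can be obeyed together. Nor does the cap change the dose for everyone above 200/110 = 1.82 m². Section 5.2.2 adds that "The doses may be rounded to the nearest 40 mg to accommodate tablet strengths", and with that rounding the doses part only from about 220/110 = 2.0 m². At 1.9 m², for example, 209 mg becomes 200 mg either way. This is at most a missing cross-reference.

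**Conclusion.** The ABT-414 point holds. Within section 5.5.1, text and table disagree on whether 1.0 mg/kg is a permitted restart dose after grade 4 toxicity in adults. At a first event the gap is 1.0 against 0.75 mg/kg. It applies to toxicities without their own rule and, by cross-reference, to skin toxicity of grade 3 or higher when the event is grade 4. This rests only on the printed wording and on 1.0 mg/kg being the adult starting dose, which the documents state consistently.

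The lomustine point is a clarification: a second grade 3 or 4 haematological event meets two sentences with different consequences, and the number of dose levels announced does not match the table.

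A reader might go further and infer a distorted overall survival comparison. The documents give no basis for that. The lomustine wording touches only Arm 3A, a subset of one arm; no frequency of the relevant events is given; and no effect on survival can be derived. The reason to act is that an operative safety rule should read one way.

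**What to change.** Reconcile the grade 4 sentence and the Dose Modification Table in section 5.5.1 so that one instruction remains, and check that the cross-reference from 5.5.1.2 still leads to it. In 5.5.2.1.1, state how the reduction sentence and the recurrence sentence interact when a grade 3 or 4 haematological event recurs, and whether recurrence means the same cytopenia or any. In 5.5.2.1, make the stated number of levels agree with the table. The clinical team must decide which statement stands in each case; this review takes no position on the dose or the rule.

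The cost is a protocol clarification and a notice to sites. Sample size, power, alpha and the planned analyses are unchanged. SAP section 9.1 already summarises dose modifications by cycle; a listing of the restart dose after each grade 4 event would show whether the ambiguity had any effect in practice.

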5.5.1.1 Allergic reactions

Subjects will be closely monitored for treatment-related adverse events, especially allergic reactions during all infusions. For the initial ABT-414 infusion, pre infusion vital signs should be taken and direct observation is required for the first 15 minutes of the infusion. Also for the initial ABT-414 infusion, subjects must remain at the site for monitoring for 60 minutes post infusion. For subsequent infusions, post-infusion monitoring is not required; however, pre-infusion vital signs should still be taken. Longer observation periods and more frequent vital sign checks may be required in subjects who experience infusion reactions.

Institutional standards should be used to treat all allergic reactions.

5.5.1.1.1 Severe allergic reactions (grade 3 or grade 4)

These require the immediate interruption of ABT-414 treatment and discontinuation from the study. Appropriate medical therapy including epinephrine, corticosteroids, intravenous antihistamines, bronchodilators, and oxygen should be available for use in the treatment of such reactions. Subjects should be carefully observed until the complete resolution of all signs and symptoms.

5.5.1.1.2 Moderate allergic reactions (grade 1 or grade 2)

These will also require the immediate interruption of ABT-414 treatment. Once symptoms have resolved, retreatment is allowed with an infusion over 60 to 70 minutes. All subsequent infusions will also be administered over 60 to 70 minutes.

5.5.1.2 Dermatologic toxicities

Subjects developing dermatologic toxicities while receiving ABT-414 should be monitored for the development of inflammatory or infectious sequelae, and appropriate treatment of these symptoms initiated. In subjects with mild and moderate (grade 1 or grade 2) skin toxicity, treatment should continue without dose delay or modification. Treatment with topical and/or oral antibiotics should be considered.

If a subject experiences severe (grade 3 or grade 4) acneiform rash, ABT-414 treatment adjustments should be made based on a discussion between the investigator, the AbbVie medical monitor and the EORTC HQ team.

Subjects who experience a grade 3 or higher dermatological toxicity will be treated as following: The subject will require a dose interruption and ABT-414 may be reintroduced at a reduced dose (per the guidance previously stated above) if the toxicity returns to \leq grade 1 within 4 weeks.

